Title: Dietary Management of Gestational Diabetes Mellitus

NCT ID not yet assigned

Document date: 2021.11.23

Study protocol

Participants

The target population was selected from 48 patients with gestational diabetes mellitus attending the obstetrics outpatient clinic of the Affiliated Hospital of XXX. The study objects were selected by non synchronous control, for example, patients who visited the hospital in the first week were included in the control group, and patients who visited the hospital in the second week were included in the experimental group until saturation.

Intervention

The intervention group

The intervention group received a 12-week dietary management intervention based on the nudge strategy. The MINDSPACE framework was used, which has nine intervention categories. Face-to-face intervention and telephone follow-up were used to provide targeted dietary management.

The control group

During the intervention, patients in the control group received routine obstetric health education and instruction under contamination, but no additional information on dietary management based on nudge strategies.

Statistical analysis plan

Data collection

From October 21, 2022 to December 31, 2022 (prospective), data was collected. At the time of enrollment, demographic information about the study participants was gathered. Pre-intervention, 1-month post-intervention and 3-months post-intervention, patients' glucose level indicators (FPG, 2hPG) and pregnancy outcomes were collected. The study subjects had no knowledge of group assignments.

Statistical analysis

All statistical analyses were carried out using SPSS, version 26.0 (SPSS Inc., Chicago, IL, USA). Continuous variables with normal distributions were expressed as $x \pm s$ and compared between groups using the independent samples t-test; continuous variables with non-normal distributions were expressed as M (Q1, Q3) and compared

between groups using the Wilcoxon rank sum test; categorical variables were expressed as cases (%) and compared between groups using χ^2 test and categorical variables were described as percentages and compared using chi-square test. Metrics that are repeated the time effect, the main effect of the intervention, and the interaction effect of both FBG and 2hPG before, 1 month after, and 3 months after the intervention were all compared in the two groups using ANOVA. $P < 0.05$ with two tailed significance was considered statistically significant.

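### The three-visit ANOVA in SPSS, with no analysis set or missing-data rule, would by default use only women with all three glucose values; a mixed model should replace it

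*Combined protocol and SAP*

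**What the plan says.** The Participants section gives one number: "The target population was selected from 48 patients with gestational diabetes mellitus". Allocation alternates by calendar week and is not randomised; for example, "patients who visited the hospital in the first week were included in the control group".

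Under Data collection, the measurement schedule is: "Pre-intervention, 1-month post-intervention and 3-months post-intervention, patients' glucose level indicators (FPG, 2hPG) and pregnancy outcomes were collected".

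Under Statistical analysis, the longitudinal comparison is described as "Metrics that are repeated the time effect, the main effect of the intervention, and the interaction effect of both FBG and 2hPG", with the values before, at 1 month and at 3 months compared between the arms by ANOVA ("the interaction effect of both FBG and 2hPG before, 1 month after, and 3 months after the intervention were all compared in the two groups"). I take FPG and FBG to be the same fasting measurement. The software is SPSS 26.0; the procedure within it is not named. An independent-samples t-test, a Wilcoxon rank sum test and a chi-square test are planned separately, without being tied to particular visits.

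The document has no definition of an analysis population, no rule for missing values, no allowance for dropout, no statement on measurement after a woman stops the programme, nothing on glucose values after delivery, and no sensitivity analysis.

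**The concern.** Time, group and interaction effects from an ANOVA on three repeated values describe the standard repeated-measures procedure in SPSS. It needs a complete row for each subject. A woman with baseline and 1-month values but no 3-month value contributes nothing to that outcome's model.

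This is the only analysis in the plan that tests whether glucose changes differently over time in the two arms, so its population matters. Three features make missing values worth planning for:

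- Only one arm carries a 12-week programme ("Face-to-face intervention and telephone follow-up were used to provide targeted dietary management"), so reasons for missing a visit could differ between arms.
- The participants are pregnant and are followed to 3 months, so delivery before the last measurement is foreseeable.
- Allocation by week gives no randomised comparison to begin with. Selective loss would add to whatever imbalance is already there.

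At stake are precision, because collected data are thrown away, and the validity of the comparison, because completers in one arm may not be comparable with completers in the other.

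**Working it through.** **Inputs from the documents.** N = 48; three measurement times; ANOVA with time, group and interaction; SPSS 26.0; two-sided 5% level. The plan gives no power, effect size, SD or dropout rate, so the 48 cannot be reproduced.

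**Assumptions.** Baseline is always measured. Each follow-up visit is missed independently with probability m. The arms are equal (24 each), since the split is not stated.

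**1. Women and values kept.**
- Complete cases = 48 × (1 − m)²
- Values collected = 48 × [1 + 2(1 − m)]
- Values used = 3 × complete cases

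For m = 10%: 48 × 0.81 = 38.9 women; collected 48 × 2.8 = 134.4; used 116.6; discarded 17.8, or 13.2%.

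| m per visit | Complete cases | Values collected | Values used | Discarded |
|---|---|---|---|---|
| 5% | 43.3 | 139.2 | 130.0 | 9.2 (6.6%) |
| 10% | 38.9 | 134.4 | 116.6 | 17.8 (13.2%) |
| 15% | 34.7 | 129.6 | 104.0 | 25.6 (19.7%) |
| 20% | 30.7 | 124.8 | 92.2 | 32.6 (26.2%) |

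If instead a share m drops out once and for all, 48 × (1 − m) women remain: 45.6, 43.2, 40.8 and 38.4.

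**2. Rough effect on power.** With 24 per arm and 80% power, the detectable standardised difference at a single visit is (1.960 + 0.842) × √(2/24) = 0.81. This is back-solved and is not the plan's figure. Holding it fixed, completers only give 76%, 71%, 66% and 61% power for the four rows. Using all women seen at a visit, 48 × (1 − m), gives 78%, 76%, 73% and 71%. The gap between the two series is the part due to listwise deletion; the rest is lost because the values were never collected.

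**3. Can completers mislead?** A simulation used 400,000 women per arm, three visits, SD 1, correlation 0.6 and no true effect. The third value was missing in the intervention arm only, more often when the 1-month value was high.

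| Overall loss in that arm | Completer difference: baseline / 1 month / 3 months (SD) | Average | 3 months, using all observed values |
|---|---|---|---|
| 10% | −0.056 / −0.093 / −0.058 | −0.069 | −0.004 |
| 20% | −0.105 / −0.176 / −0.101 | −0.127 | 0.004 |
| 30% | −0.152 / −0.251 / −0.152 | −0.185 | −0.001 |

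The last column predicts the missing values from the earlier ones, which is valid under missing at random. The false signal appears in the group main effect and in the change to 1 month (at 20% loss, −0.176 + 0.105 = −0.071). The change from baseline to 3 months is almost untouched (−0.101 + 0.105 = 0.004). The sign comes from the assumed pattern: if women with low values were lost instead, it would reverse.

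**4. Dates that bear on the third value.** From 21 October to 31 December 2022 is 10 + 30 + 31 = 71 days; the programme lasts 12 × 7 = 84 days. If that window is meant to hold both enrolment and all follow-up, no woman enrolled in it finishes the programme inside it. The document does not say whether that is meant. Nor does it say whether 3 months counts from the start or the end of the programme. Neither point enters the counts above.

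**The case against.** The best defence is that the plan never states listwise deletion. It says ANOVA, SPSS 26.0 also has a mixed-model procedure that keeps incomplete cases, and with no missing values the issue disappears. That is fair: deletion is the default reading and not a declared rule, and actual missingness is unknown. But a plan should not leave the population of its only longitudinal test to a software default.

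A second objection is that a mixed model does not solve early delivery. This also stands. After delivery the pregnancy glucose value does not exist, and a likelihood model would in effect extrapolate it. What is to be compared must be defined; choosing a model does not settle it.

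Several stronger readings are tempting, and the documents do not support them:

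- **That women who stop the programme are dropped, or are no longer measured.** A woman who stops but has all three values stays in the model. The schedule carries no condition on adherence; continued measurement is simply not addressed.
- **That an incomplete woman loses all her data.** This holds only for the repeated-measures model. The t-test, Wilcoxon and chi-square comparisons can use whatever was observed.
- **That the bias favours the intervention.** No dropout figures, reasons or split by arm are given, and control women can miss visits too. The simulated values follow from the pattern assumed.
- **That about half the women would be lost through delivery before 3 months.** The documents give no gestational age at entry or delivery, and the timing of the last visit is ambiguous, so no figure can be defended.

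**Conclusion.** The point holds in a limited form. The plan specifies a three-time ANOVA without an analysis set or missing-data rule, and the usual SPSS procedure would confine each glucose model to women with all three values. Under independent misses of 5% to 15% per follow-up visit, about 43 to 35 of 48 women remain and about 7% to 20% of the collected values are discarded. These rates are assumptions. Bias is possible if missingness differs by arm or depends on earlier glucose; its size and direction cannot be stated in advance. The change is worth making because the replacement keeps partial data, rests on a weaker assumption about missing values and is available in the named software. Confidence is medium, because actual missingness is unknown and the procedure is not named.

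**What to change.** In the Statistical analysis section:

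1. Replace the ANOVA for fasting and 2-hour glucose with a linear mixed model for repeated measures (SPSS MIXED) with group, visit and group-by-visit as fixed effects and an unstructured covariance. Three visits need 3 × 4 / 2 = 6 covariance parameters.
2. Define the analysis set as every enrolled woman with any glucose value, in the group to which her week of attendance assigned her.
3. State that fasting and 2-hour glucose continue to be collected, and are used, after a woman stops the programme.
4. State whether values after delivery belong to the comparison. If they do not, label those visits as not applicable and say how the 3-month comparison is then defined, so that the model does not silently extrapolate past delivery.
5. Report missing values by arm and visit, with reasons.
6. Add a simple sensitivity analysis that departs from missing at random, such as shifting the imputed values in one arm over a stated range.

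In Data collection, say from when the 1-month and 3-month visits are counted, and reconcile the 71-day window with the 84-day programme and the last visit.

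The cost is SAP wording, slightly more analysis work and the effort of keeping measurements going. If no value is missing, the estimated group means at each visit are the same as under the ANOVA. The remaining limitation is that the mixed model still assumes data missing at random, which is why item 6 is needed.
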